2. STUDY OBJECTIVES

2.1. Primary Objective

The primary objective of the study is:

- To determine the efficacy of NOVOTTF-200A in recurrent anaplastic astrocytoma patients (6-month progression-free survival).

2.2. Secondary Objectives

The secondary objectives of the study are:

- To evaluate the safety of NOVOTTF-200A in the subject population.
- To evaluate efficacy of NOVOTTF-200A in the subject population.
- To see if the presence of ATRX, TERT promoter, MGMT methylation and/or IDH1 mutation, confers a better response to NOVOTTF-200A.
- To determine if the treatment significantly modifies the patient's quality of life. We will use the Functional Assessment of Cancer Therapy (FACT) questionnaires:
 - FACT-Brain (FACT-Br)
 - FACT-Cognitive Function (FACT-Cog)

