Background and Study Rationale	
The study population includes subjects with histologically confirmed recurrent/progressive anaplastic astrocytoma (G3 astrocytoma). The population includes patients who had progressive disease after treatment with radiation, followed by either temozolomide chemotherapy or CCNU or PCV or other clinically available agents (cyclophosphamide, etoposide). These patients must not have previously received any bevacizumab (BEV) or any experimental agents.
 
At the time of recurrence after temozolomide, the patients have no standard of care choices. They are treated with a variety of different treatments based on the treating physician choice. Most frequently, the chosen regimen includes bevacizumab based on the published data showing a 6-month progression-free survival of 55% (95% CI, 36-70%) and 6-month overall survival of 79% (95% CI, 61-89%). Additional treatment options are needed for these subjects.
 
Published literature indicates that targeting mitosis via tumor treating fields (TTF) in rapidly dividing cancer cells by disrupting both spindle formation and normal cytokinesis selectively kills or arrests growth in glioma cell lines. The NovoTTF-200A® system is a novel antimitotic cancer therapy approved in 2011 by the FDA for the treatment of recurrent (supratentorial) glioblastoma (G4 astrocytoma) based on the results of a Phase 3 trial comparing NovoTTF® therapy with best active chemotherapy according to physician choice. No data are currently available on the response of anaplastic astrocytoma to this technology. In addition, no biomarker is yet available in order to predict which patients will have a better response to the NovoTTF® technology.
 
The NovoTTF device-related adverse effect most commonly cited involves skin irritation and heat sensations on the scalp below the transducer arrays.

	
Patients described these as “warm,” “tingling” sensations, none of which were associated with injury to the patient. Systemic events which were often associated with chemotherapy (gastrointestinal, hematologic and infectious adverse events) are rarely reported with use of NovoTTF.

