6.3. Method of Treatment Assignment

Single arm study. All the patients will receive NOVOTTF-200A treatment.

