Design: This is a single-center, single-arm, open-label, Phase-IIA clinical trial to estimate PFS₆ under the conditions of the trial and to gather information on safety and tolerability associated with the device in clinical use.

8.1. Sample Size: Justification of Sample Size: Data from 36 participants will yield a 90-percent interval estimate of PFS₆ with sufficient precision for our purposes. Table 1 shows the probability of observing a 90-percent confidence interval from 34 participants at various levels of the population proportion and confidence-interval half widths. The table is based on 34 rather than 36 participants, anticipating some loss of participants to the exigencies of research.

The table shows over 90-percent power to estimate PFS₆ to plus or minus 16 percent at all levels of the population proportion shown. The power to estimate PFS₆ to plus or minus 15

percent is adequate for the more extreme levels of population proportion, but perhaps not when the latter is near 50 percent.

Table 1. Probability of Observing a 90-Percent Binomial Confidence Interval Given 34 Subjects for the Indicated Underlying True Proportions and Interval Half Widths

Population Proportion	Interval Half-Width		
	13%	15%	16%
25%	0.36	0.99	0.99
35%	0.05	0.83	0.99
45%	0.00	0.47	0.99
55%	0.00	0.47	0.99
65%	0.05	0.83	0.99
75%	0.36	0.99	0.99

Rounded to nearest one hundredth, exact method, 2-sided, SAS Power and Sample Size v3.1

Futility Assessment. If none of the first nine participants is progression-free at six months from initial use of the device, then serious consideration will be given to stopping the project for futility. This criterion is adopted from the Simon, two-stage, optimal design (null-hypothesis rate of 5% v alternate- hypothesis rate of 25%). A formal decision to stop the trial will depend upon the clinical judgment of the medical director.

Intolerability Assessment. Intolerability and adverse events will be closely monitored by the treating physicians. A decision to stop the project for intolerability will be based on clinical judgment of the medical director.

Primary Analyses for Efficacy: The 90-percent interval estimate of PFS6 is the primary summary of efficacy in this project. Exact methods will be used.

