Secondary Analyses for Efficacy: We will examine the data in many ways to inform decisions about further research, including plots, tables, and statistical tests, accounting for repeated measures where appropriate. Participants will be described by sex, age, and other host or clinical factors, using means, medians, and percentiles for continuous variables and counts and percentages for categorical variables. The FACT-Br and FACT-Cog will be scored in the standard way (Weitzner et al, 1995). Both progression-free and overall survival will be estimated by Kaplan-Meier methods, both overall and by strata of interest. Differences in survival between or among groups will be evaluated by the log-rank test. If the assumptions are reasonably met, then Cox proportional-hazards models will examine the effects on survival of covariates adjusting for other covariates. Ties in survival time will be broken by the subtracting a small, randomly generated amount from each tied observation (Borucka, 2014). Secondary analyses will be performed on both the ITT and PP data sets, as seems warranted. For secondary analyses, the probability values from statistical tests will be used as a guide to interpretation, which will also depend on clinical judgment. Therefore, we will not be concerned with overall, study-wise, type-1 error rates for the secondary analyses.

Analyses for Intolerability or Toxicity: We will examine the data to discover factors that may predict adverse reactions to the study treatment. We will proceed in the same way as outlined

above for secondary analyses for efficacy. As the goals of these analyses are to inform decisions about future research, no formal statistical hypothesis testing will be done, probabilities from statistical tests will augment clinical judgment in interpretation, and we will not regard overall, study-wise, error rates.

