9. OUTCOME MEASURES

9.1. Efficacy Analysis

Tumor response including PD, progression-free survival (PFS), and overall survival (OS) will be assessed by the investigators using RANO 2010 criteria. The overall confirmed response rate will be examined.

Efficacy analysis:

Primary Endpoint

- *The primary endpoint of the study will be 6-month progression-free survival*

Secondary Outcome Measures

- *Safety*
- *Overall survival time*
- *Correlations with established molecular markers (ATRX, TERT promoter and/or IDH1 mutation and MGMT promoter methylation)*
- *Quality of Life*

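### The marker and phenotype objectives ask who benefits from the device, which a single-arm trial cannot answer; restate them as association with outcome in treated patients

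*Combined protocol and SAP*

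**What the plan says.** Section 2.2 and the synopsis list, as a secondary objective, whether ATRX, TERT promoter or IDH1 mutation or MGMT promoter methylation "confers a better response to NOVOTTF-200A". Section 2.3 and the synopsis put the same question, as exploratory, for the proneural or mesenchymal phenotype. The synopsis rationale gives the gap to be filled: "no biomarker is yet available in order to predict which patients will have a better response to the NovoTTF® technology".

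On design, section 6.3 reads: "Single arm study. All the patients will receive NOVOTTF-200A treatment". Section 8 calls the study a "single-center, single-arm, open-label, Phase-IIA clinical trial to estimate" PFS6. No control group and no external reference by marker is planned.

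On analysis, section 8.1 (Secondary Analyses for Efficacy) has PFS and OS estimated by Kaplan-Meier "both overall and by strata of interest", then: "Differences in survival between or among groups will be evaluated by the log-rank test". Cox models may follow. These sentences name no marker, but no other secondary efficacy analysis is described. Response is not defined for the marker objective.

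Other sections are softer. Section 9.1 lists "Correlations with established molecular markers" as the outcome measure. Section 4 (Gene Profiling) speaks of phenotypes being associated with response. Section 8 lists mutation status among variables for exploratory use. Section 8.1 treats secondary p-values as an interpretive guide without study-wise error control.

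**The concern.** To say that a marker makes patients respond better to a device is to say that the device does more for carriers than for non-carriers. That is a treatment-by-marker effect, and estimating it needs to know how carriers and non-carriers fare without the device. Here nobody goes without it. A marker that only tracks natural history gives the same pattern among treated patients as one that truly selects device responders.

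The protocol knows the distinction. Section 1.1 describes the 1p19q codeletion as predictive of treatment response and, separately, as prognostic for survival. Nothing comparable is said of the four study markers. OS is harder still to read as response to the device, because under section 3.1 the device stops at radiological progression and the investigator chooses another treatment.

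What is at stake is the conclusion drawn for a stated secondary objective. If it is answered in its own words, a difference between marker groups becomes a statement about who benefits from the device, and these analyses are meant to inform further research.

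**Working it through.** **1. The plan's own figures.** The plan gives no effect size, alpha or power for the marker objective. Its only sample-size figures are the PFS6 precision table in section 8.1. Exact (Clopper-Pearson) 90% limits with n = 34, summing binomial probabilities over outcomes whose half-width is within 13%, 15% or 16%, give:

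| True PFS6 | Recomputed | Printed |
|---|---|---|
| 25% (or 75%) | 0.357 / 0.988 / 1.000 | 0.36 / 0.99 / 0.99 |
| 35% (or 65%) | 0.053 / 0.830 / 1.000 | 0.05 / 0.83 / 0.99 |
| 45% (or 55%) | 0.003 / 0.468 / 1.000 | 0.00 / 0.47 / 0.99 |

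The table reproduces to about 0.01, so n = 34 is used below. It says nothing about markers.

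**2. What one arm identifies.** Let h be the hazard in untreated marker-negative patients, θ the device hazard ratio in marker-negative patients, γ the marker's prognostic hazard ratio, and δ the ratio of device hazard ratios (marker-positive over marker-negative). The objective is about δ.

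- Treated, marker-negative: hθ
- Treated, marker-positive: hθγδ
- Ratio seen in this trial: γδ

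A ratio of 0.5 arises from γ = 0.5, δ = 1 (purely prognostic) and equally from γ = 1, δ = 0.5 (purely predictive). Only untreated patients would supply γ. Adjusting a Cox model for other covariates does not supply it. The same gap applies to tumour response, which also has no untreated comparison.

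**3. Simulation.** Assumptions: n = 34, exponential times, marker-negative median 6 months, cut-off 24 months, two-sided 5% log-rank test, 4,000 runs. Rejection rates:

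| Marker-positive share | Prognostic only, HR 0.5, no device effect | Predictive only, device halves hazard in carriers | Inert marker |
|---|---|---|---|
| 50% | 45.4% | 45.3% | 6.1% |
| 30% | 36.1% | 36.8% | 5.5% |

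The second and third columns agree within simulation error because the two mechanisms generate the same data. A separate simulation (17/17 split, median 4 months, 18 months of follow-up, 2,000 runs, no device effect) gave 29%, 45% and 68% at prognostic hazard ratios of 0.6, 0.5 and 0.4, and 5.4% for an inert marker.

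**4. Check by formula.** Schoenfeld power for an even split is Φ(√(d/4) × |ln HR| − 1.96), with d events. In step 3 the expected events are 17 × (1 − 2⁻⁴) + 17 × (1 − 2⁻²) = 17 × (0.9375 + 0.75) = 28.7. With HR 0.5: √(28.7/4) × 0.693 − 1.96 = −0.10, and Φ(−0.10) = 46%, in line with the simulation. With 34, 26 and 20 events the formula gives 52%, 42% and 34%. Section 5.2 admits patients without archival tissue, so the marker-known number may be below 34 and the rate correspondingly lower.

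**5. What a real test would need.** With a control arm, four equal cells and an assumed δ of 0.5, 80% power at two-sided 5% needs four times the events of a two-group comparison. The two-group figure is 4 × (1.96 + 0.84)² / (ln 0.5)² = 65.3, so 66 events; 4 × 66 = 264. At most 36 patients will be enrolled, so the question cannot be rescued within this trial.

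**The case against.** The strongest reply is that the plan never says what a critic fears. Section 8.1 does not name the markers as log-rank groups. It sets no alpha or success criterion for them, and p-values are guides alongside clinical judgement. Section 8 calls the use of mutation status exploratory, and sections 4 and 9.1 already speak of association and correlation. A reader might infer that a significant log-rank test will be credited to the device and used to select patients. The documents do not support that: they contain no such rule, and the link from markers to log-rank groups is itself an inference. A reader might also infer that the four markers are known to be prognostic. The documents do not say so, and every hazard ratio above is assumed.

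It can also be said that the objective refers to response, which section 8 measures separately as partial and complete response. If RANO response is meant, natural prognosis is a weaker rival explanation than it is for PFS or OS, and a log-rank simulation does not address it. That is fair, but the plan leaves the term open and plans no untreated comparison for any of the three outcomes.

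These points limit the consequence and the size. They do not remove the mismatch. Calling an analysis exploratory guards against over-reading chance findings; it does not make δ estimable. The synopsis and sections 2.2 and 2.3 still pose a question that the softer sections do not claim to answer.

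**Conclusion.** The point stands as a mismatch between objective and design. The marker and phenotype objectives ask for a device-specific effect, and a trial in which everyone is treated can show only association with outcome under treatment. That conclusion rests on the design alone and on no assumed hazard ratio.

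The size is illustrative: about 45% rejection for a purely prognostic marker with an assumed hazard ratio of 0.5, all 34 patients marker-known and evenly split, at two-sided 5%. It is lower with uneven groups or missing tissue, and about 6% if the marker is inert. It should not be read as the plan's expected rate of false claims, since the plan sets no threshold and the markers' prognostic effects are not given. The primary PFS6 interval estimate is unaffected.

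The opposite error should be avoided too. The same argument that rules out calling these analyses predictive rules out calling them prognostic.

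**What to change.** 1. In the synopsis and sections 2.2 and 2.3, restate the marker and phenotype objectives as whether the marker *is associated with outcome (tumour response, PFS, OS) in patients treated with NOVOTTF-200A*. This agrees with the language of sections 4 and 9.1, keeps tumour response in the objective, and settles what response covers.
2. Add one sentence to section 8.1: these analyses cannot distinguish prognostic from predictive effects, and no differential device benefit will be concluded from them. Do not label them prognostic.
3. In section 8.1, name the marker and phenotype groups among the strata, and report each group's estimates with confidence intervals and the number with known status.

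No patients, visits or data are added. The sponsor gives up only a claim that this design could not support.

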2.3. Exploratory Objectives

The exploratory objectives of the study are:

- To determine if the presence of proneural or mesenchymal phenotype (Cytoscan analysis) confers a better response to NOVOTTF-200A.
- To determine if the *in vitro* sensitivity of the glioma cells derived from patient specimens before and after the NOVOTTF-200A treatment correlates with the patient's response to treatment.

3. OVERALL STUDY DESIGN

3.1. Study Design

This is a Phase 2, single arm study in subjects with AA who had progressive disease during first-line treatment or who are in first or second relapse and who have not previously received any bevacizumab (BEV) or other anti-angiogenic agent, including sorafenib, sunitinib, axitinib, pazopanib or cilengitide. Up to 36 subjects will be enrolled with 26 evaluable patients needed.

The determination of whether to stop treatment due to progression will be based on the investigator's evaluation of the patient's clinical condition. NovoTTF-200A treatment may be continued until disease progression, unacceptable toxicity, withdrawal of consent, or termination of the study. In the case of radiological progression, NOVOTTF-200A treatment will be stopped and a different treatment will be chosen instead by the investigator.

Patients will be recruited to the study by the principal investigator (PI) or one of the coinvestigators (CI) at UC Irvine. Patient accrual is expected to continue for 24-36 months.

NovoTTF-200A treatment will be given alone for this single arm study. At treatment initiation patients will be seen at an outpatient clinic. During this visit baseline examinations will be performed and NovoTTF-200A treatment will be initiated under medical supervision. The patients will also be instructed on the operation of the NovoTTF-200A and battery replacement. Once the patients are trained in operating the device they will be released to continue treatment at home. The patients will receive multiple 1 month courses of continuous NovoTTF-200A treatment.

NovoTTF-200A treatment will be stopped in the following cases:

1. Treatment will be stopped in the case of device related serious adverse events
2. Clinical and functional deterioration considered by the investigator to be prohibitive of continuing treatment.
3. Radiological progression
4. Re-operation, for the patients where the pathology is consistent with necrosis (pseudo-progression). NovoTTF-200A treatment will be interrupted for at least 2 weeks after reoperation or until wound healing).

As long as the patients are receiving treatment (NovoTTF-200A), all patients will be seen once every month at an outpatient clinic where they will undergo medical follow-up and routine laboratory exams. An MRI will be performed every second month following the baseline MRI.

In the case of clinical progression an unscheduled MRI will be obtained within 1 week of the investigator becoming aware of the clinical progression. No additional MRIs will be required after progression.

Medical follow-up will continue for 2 months after treatment termination in order to capture treatment related toxicities. After these visits, mortality will be assessed based on monthly telephone interviews with the patients or the patients' caregivers.

3.2. Study Design Rationale

The study is a single arm design that is often used in Phase 2 cancer studies. Standard evaluations for safety and efficacy are employed.

3.3. Study Duration

Subjects may continue on study treatment until disease progression, unacceptable toxicity, withdrawal of consent, or termination of the study. Once discontinued from the study treatment, subjects will enter a long-term follow-up period for documentation of survival and the start of first new anti-glioma therapy and its outcome. Long-term follow-up will occur every 3 months (± 7 days) after the 28-day post-treatment discontinuation visit.

3.4. End of Trial

The End of Trial is defined as the date of receipt of the last data point from the last remaining subject that is required for primary, secondary and/or exploratory analysis.

4. PROCEDURES

Study visits and procedures will be performed as outlined in Table 1.

The study will consist of Screening, Treatment, and Follow-up periods.

Screening:

Screening procedures may not be done prior to the signing and dating of the Informed Consent document. However, the results of tumor assessments done as part of standard of care that are within the 14-day screening period do not have to be repeated. However, if results are not available, then tumor assessments are to be conducted within 14 days prior to Cycle 1 Day 1. The screening period may not exceed a 28 day (with a 3 day window for scheduling conflicts) window prior to start of study treatment (Cycle 1 Day 1) for assessments that include medical history including demographics and cancer history, prior medications and procedures. Physical examination including height, weight, and vital signs, electrocardiograms, laboratory tests including hematology, coagulation, chemistry, urinalysis, and, as appropriate, pregnancy tests are to be done within 7 days prior to Cycle 1 Day 1.

Treatment:

Safety tests and procedures will be performed according to the Schedule of Assessments and Procedures (Table 1). Assessments will include MRI scans at the end of every even numbered cycle using RANO 2010 criteria for assessment.

Subjects may continue on study treatment until disease progression, unacceptable toxicity, withdrawal of consent, or termination of the study.

End-of-Treatment Visit:

An End-of-Treatment Visit should occur when a subject discontinues study treatment 28 (+7) days after NOVOTTF-200A. Tests are primarily to ensure there are no late occurring AEs and that AEs have resolved or have stabilized. Additional follow up visits may be conducted to follow ongoing that are resolving. If a subject cannot or will not make this visit, attempts to gather information on the status of AEs should be made by telephone or other means.

Post Study Follow-up:

All subjects will be followed for survival during the follow-up period for as long as they are alive. Post Study follow-up will occur every 3 months (± 7 days) after the End-of-Treatment Visit. During long-term follow-up, the following information will be collected: survival, subsequent anti-glioma regimens, and treatment outcomes.

Efficacy Assessments

Tumor response, including progressive disease, will be assessed with MRI at the end of every 2 cycles of therapy according to the RANO criteria (Wen 2010), including:

- Radiographic Overall Response Rate
- Progression-free Survival (PFS)
- Overall Survival (OS)

Assessments

Gene Profiling

For AA subjects with available tissue, gene signature profiling will be performed, using the Cytoscan analysis. We will determine the GBM phenotype (mesenchymal versus neuronal) and will see how that the particular gene phenotypes associate with response to treatment

In-vitro Sensitivity of glioma cells derived from patient specimens

For AA subjects resected in our center, primary cell cultures will be produced. The response to TTF fields in the Inovitro system will be compared between patients, before and after the NOVOTTF-200A treatments – for the patients that also have surgery after progression.

Quality of Life Assessments

- **FACT-Cog**

The Functional Assessment of Cancer Therapy-Cognitive Function (FACT-Cog) is a 37-item validated subjective neuropsychological instrument designed to evaluate cancer patients' perceived cognitive deterioration on their quality of life. A 6.9 to 10.6 points reduction of the FACT-Cog score corresponds to the smallest clinically-relevant perceived cognitive deterioration. These estimates are important as they can facilitate the interpretation of patient-reported cognitive changes and sample size estimation (Chan 2013). The FACT-Cog questionnaire is provided in Appendix B.

- **FACT-Br**

The Functional Assessment of Cancer Therapy-Brain (FACT-Br) is a commonly used instrument measuring general quality of life (QOL) that reflects symptoms or problems associated with brain malignancies across 5 scales. The measure yields information about total QOL, as well as information about the dimensions of physical well-being, social/family well-being, emotional well-being, functional well-being, and disease specific concerns. The FACT-Br is written at the 4th grade reading level, and subjects can filled out it in 5-10 minutes. The self-report of quality of life can be completed by the subject or with little or no assistance in subjects who are not neurologically incapacitated. Subjects rate all 5 items using a five-point Likert scale ranging from 0 (not at all) to 4 (very much). Overall, higher ratings suggest higher QOL. Items are totaled to produce the following subscales, along with an overall QOL score: physical well-being (7 items); social/family well-being (7 items); emotional well-being (6 items); functional well-being (7 items); and concerns relevant to subjects with brain tumors (23 items). The FACT-Br questionnaire is provided in Appendix C (Cella 1993).

